7.1. Disposition of Subjects and Withdrawals

The numbers of subjects enrolled, completing, and withdrawing, along with reasons for withdrawal, will be tabulated by duration of time in the study. Data will also be presented in a by-subject listing.

7.2. Protocol Violations and Deviations

Protocol deviations will be identified via the eCRFs and classified as important or non-important. Data will also be presented in a by-subject listing.

7.3. Demographics and Other Baseline Characteristics

Demographic variables will include race, ethnicity, age, age categories (18-35 years, 36-55 years, 56-65 years), sex, height, weight, and body mass index (BMI). Age will be calculated as an integer in years as the difference between the subject's date of informed consent and the date of birth. Demographic and baseline characteristic data will be summarized. Data will also be presented in a by-subject listing.

Prior medications will be summarized, by the number and percentage of subjects taking each medication and classified by ATC class and preferred term. This analysis will be conducted for the Safety population. Data will also be presented in a by-subject listing, which will include ATC Level 2 classification, preferred name, and verbatim name.

Medical and psychiatric history will be summarized for the Safety population classified by system organ class (SOC) and preferred term. Data will also be presented in a by-subject listing, which will include SOC, preferred term, and the verbatim term.

Results from the Mini-International Neuropsychiatric Interview (MINI) will be presented in a by-subject listing.

7.4. Exposure

PH94B will be supplied in [REDACTED] Each spray delivers 1.6 µg per 100 µL spray. At Visit 2 (Baseline) and each monthly Visit thereafter, site personnel will instruct the subject to self-administer the IP by 1 spray into each nostril (right and left nasal passages), for 2 total sprays per dose up to 4 times per day.

Number of days of exposure to PH94B (date of Visit 14 (or completion date) minus date of Visit 2 (Baseline)) will be summarized overall. Average difference in vial weights at each visit (for all subjects completing each visit) will be summarized overall.

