### 9.1. Identification of Investigational Product

The IP (PH94B Nasal Spray) is supplied in a 10-mL amber glass vial with a spray actuator. The spray actuator has a clear protective cover.

PH94B is odorless and contains propylene glycol, ethyl alcohol, polysorbate 80, water (q.s. to 100%), and benzalkonium chloride as a preservative, in a phosphate buffer.

PH94B will be supplied in monthly kits consisting of a sufficient number of 10-mL amber glass vials, where each vial contains 8 mL of PH94B. Each metered dose spray delivers 1.6  $\mu$ g per 100  $\mu$ L spray. There is sufficient volume in each vial to deliver at least 60 sprays of PH94B.

Use of the i.n. route is essential given the site of action of PH94B on nasal sensory chemoreceptors (see Section 5.1).

PH94B will be supplied by [REDACTED]

New vials should be allowed to come to room temperature for 30 minutes and primed before use according to the instructions provided.

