### 9.2. Selection of Timing of Dose for Each Subject

The IP will be administered once in each nostril. Men and women will be treated with the same 3.2- $\mu$ g dose of PH94B. Each nasal spray delivers 100  $\mu$ L containing 1.6  $\mu$ g PH94B. [REDACTED]

Treatment with PH94B should be self-administered approximately 15 minutes prior to or during an anxiety-provoking social situation or event. Consecutive nasal administrations of IP should be at least 1 hour apart, with no more than 4 administrations per day.

Site personnel will instruct the subject to self-administer the IP by 1 spray into each nostril (right and left nasal passages), for 2 total sprays per dosing event.

Subjects are instructed to record all PH94B administrations in the provided eDiary, even if they have not used PH94B that day (see Section 9.4.1).

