### 9.4. Treatment Compliance

Study personnel will weigh each vial of IP prior to dispensing to subjects and upon return of used or unused vials of IP from subjects to the study personnel. Vial weights will be documented in the eCRF. Subjects will record their use of the IP in an eDiary during the study (see Section 9.4.1).

Subjects will self-administer the IP up to 4 times per day between visits. The study personnel will be responsible for reviewing the self-administration of the IP in the eDiary.

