Subjects will be instructed to return to the clinic for Visit 3 after 30 days (± 3 days). At Visit 3, subjects will undergo clinical laboratory assessments (clinical chemistry, hematology, urinalysis, pregnancy test, and urine drug screening), vital signs, 12-lead ECG, physical examination, HAM-D17, [REDACTED] LSAS, C-SSRS, CGI-S, CGI-I, and self-evaluation by the patient-reported outcome measure, Patient Global Impression of Change (PGI-C). At Visit 3, PH94B use recorded in the eDiary application will be reviewed and AEs and concomitant medications will be reported and recorded. Subjects will receive a 1-month supply of PH94B (6 vials).

Subjects will return to the clinic at monthly intervals (± 7 days, Visits 4 to 13), and will repeat the same assessments as those performed at Visit 3. PH94B use recorded in the eDiary application will be reviewed, AEs and concomitant medications will be reported and recorded, and at each Visit subjects will receive a 1-month supply of PH94B (6 vials).

At Visit 14 (1 year ± 2 weeks), treatment will conclude, and subjects will undergo clinical laboratory assessments (clinical chemistry, hematology, urinalysis, pregnancy test, and urine drug screening), vital signs, 12-lead ECG, physical examination, HAM-D17, [REDACTED] LSAS, C-SSRS CGI-S, CGI-I, and PGI-C. Also, PH94B use recorded in the eDiary application will be reviewed, and AEs and concomitant medications will be recorded and reported. Subjects will also be informed of their follow-up Visit (Visit 15).

Subjects will return to the clinic for a follow-up Visit (Visit 15, 54 weeks ± 3 days), approximately 2 weeks after the last PH94B administration, to undergo C-SSRS and vital signs assessments, and record AEs.

Safety Considerations:

Safety and tolerability of PH94B (≤ 4 doses per day up to 12 months in up to 600 subjects) will be assessed and summarized through changes from baseline (Visit 2) to end of treatment (Visit 14) in AEs, laboratory values, 12-lead ECGs, physical examinations, and vital sign assessments following exposure to PH94B.

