8.9. Coronavirus 2019 (COVID-19) Impact

The SARS-CoV-2 virus and variants may still be a threat and safety precautions may still be in place during study enrollment. To assess the impact of the COVID-19 pandemic on study

AD-ST-33.06 Effective date: 12-Nov-2020

procedures, study staff will complete the COVID-19 Impact questionnaire. Should a study Visit be affected by COVID-19, study staff will record how the Visit was affected (missed, abbreviated, delayed, performed remotely, or otherwise deviating from the planned format in the protocol) and which procedures were impacted. All COVID-19 protocol deviations will be provided in a separate listing. This listing will include the subjects, affected Visits, and affected assessments.

10. Changes from Planned Analysis

Endpoints removed: analysis not performed – data not collected.

Study staff will complete the Coronavirus 2019 (COVID-19) Impact questionnaire to assess the impact of the COVID-19 pandemic on study procedures. The COVID-19 Impact questionnaire is described in Section [8.9](#). All COVID-19 protocol deviations will be provided in a separate listing.

Exploratory objectives (changes in pattern of PH94B use daily frequency and dosing interval) requiring the use of eDiary data were removed due to unreliability of eDiary data.

The original planned interim safety analysis was removed from the study.

A qualitative review of categorical data was done instead of an assessment of a change in proportion over time due to limited availability of data.

11. References

ASA. (2018) Ethical Guidelines for Statistical Practice. Prepared by the Committee on Professional Ethics, April 2018. <http://www.amstat.org/about/ethicalguidelines.cfm>

Carpenter JR and Kenward MG. *Multiple Imputation and its Application (Statistics in Practice)*. Chichester, West Sussex, UK: John Wiley & Sons; 2013.

Graham JW, and Olchowski AE, Gilreath TD. (2007) “How Many Imputations are Really Needed? Some Practical Clarifications of Multiple Imputation Theory.” *Prev Sci.* 2007;8(3): 206-213.

ICH (1998). ICH Harmonised Tripartite Guideline. Statistical Principles for Clinical Trials E9; 1998. https://database.ich.org/sites/default/files/E9_Guideline.pdf

Little R and Rubin D. (1987). Statistical Analysis with Missing Data, New York: Wiley.

RSS. (2014) The Royal Statistical Society: Code of Conduct, 2014. <https://rss.org.uk/about/policy-and-guidelines/code-of-conduct/>.

12. Tables, Listings, and Figures

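### No planned analysis relates a subject's PH94B use to the Protocol maximum of 4 doses a day, because vial weights are never converted to doses

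*SAP*

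**What the plan says.** **The limit.** Protocol 9.2 has subjects dose themselves as needed, "with no more than 4 administrations per day". SAP 7.4 repeats this as one spray per nostril, "for 2 total sprays per dose up to 4 times per day".

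**What is collected.** Daily dose counts come from the eDiary (Protocol 9.4.1). The objective measure is weight: each vial is weighed before dispensing and on return, and "Vial weights will be documented in the eCRF" (Protocol 9.4).

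**What the Protocol promised.** Protocol 13.1.3 plans summaries of total doses and average daily doses, overall and by 3-month period. Protocol 13.1.5.1 adds a split between users at 3 or 4 times a day and users at 2 or fewer.

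**What the SAP keeps.** SAP section 10 says the objectives on changing patterns of use "were removed due to unreliability of eDiary data". It does not mention the dose summaries of Protocol 13.1.3, but they are absent. SAP 7.4 keeps days of exposure (Visit 14 or completion date minus Visit 2) and, for use, "Average difference in vial weights at each visit (for all subjects completing each visit) will be summarized overall". SAP 6.1.7.1 (General) defines use from the weights of six vials, in weight units. SAP 5 says AEs will be grouped by length of exposure and by how much PH94B was used, but it defines no levels. SAP 8.1 splits TEAEs only around Visit 14, and no AE table listed in SAP 12.3 uses a level of use.

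**Deviations.** SAP 7.2 says only that "Protocol deviations will be identified via the eCRFs and classified as important or non-important".

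**The concern.** The study is meant to describe safety with self-administered dosing up to 4 times a day. To interpret its AE rates, a reader needs to know how much drug subjects took relative to that maximum. The plan gives calendar days, which count the same for someone who dosed four times a day and someone who hardly dosed. It also gives a weight difference with no link to doses, to the maximum, or to the number of days over which the weight was lost.

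Two questions then go unanswered: how many subjects averaged more than 4 doses a day over some interval, and how many used so little that their 12 months add little information. Without a defined level of use, the AE grouping announced in SAP 5 cannot be produced in a pre-specified way.

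**Working it through.** **Inputs**
- At most 4 doses a day, 2 sprays per dose (Protocol 9.2; SAP 7.4).
- 100 µL per spray and 8 mL per vial (Protocol 9.1), so 0.2 mL per dose.
- Deliverable sprays: "There is sufficient volume in each vial to deliver at least 60 sprays of PH94B" (Protocol 9.1).
- Vials per month: SAP section 3 states "Subjects will receive a 1-month supply of PH94B (6 vials"; the current Protocol (9.1, 9.9.1) fixes no number.
- 30 days to Visit 3; later visits have a window of ±7 days (Protocol 10.2), taken here as up to about 37 days between visits.
- Density about 1 g/mL (assumption; not in the documents).

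**1. Reproduce the plan's figure.** 8 mL / 0.1 mL = 80 nominal sprays per vial. This is consistent with the stated minimum of 60 once priming and residue are allowed for.

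**2. The maximum in volume.** Over 30 days: 4 × 2 × 30 = 240 sprays = 24 mL. Over 37 days: 4 × 2 × 37 = 296 sprays = 29.6 mL.

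**3. Weight without interval length is ambiguous.** Take a loss of 27 mL after any priming correction. Over 30 days it is 27 / (0.2 × 30) = 4.5 doses a day, above the maximum. Over 37 days it is 27 / (0.2 × 37) = 3.65, below it. A minimum or maximum weight in a by-visit table cannot separate the two.

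**4. The mean conceals the tail.** If 10% of subjects averaged 6 doses a day and 90% averaged 1, the mean is 0.1 × 6 + 0.9 × 1 = 1.5. With 20% and 80% it is 0.2 × 6 + 0.8 × 1 = 2.0. Both sit well below 4. In this artificial two-level case the mean, minimum and maximum would let a reader work back to the share. With use spread over many levels, those figures and the SD do not fix the number of subjects above a threshold or near zero.

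**5. Supply against the maximum.** Ratio = (vials × sprays per vial) / (8 × days).

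| Vials | Days | At 60 sprays per vial | At 80 sprays per vial |
|---|---|---|---|
| 6 | 30 | 360/240 = 1.50 | 480/240 = 2.00 |
| 6 | 37 | 360/296 = 1.22 | 480/296 = 1.62 |
| 5 | 30 | 300/240 = 1.25 | 400/240 = 1.67 |
| 4 | 30 | 240/240 = 1.00 | 320/240 = 1.33 |

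The first row would support 360 / (2 × 30) = 6 to 480 / (2 × 30) = 8 doses a day.

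**6. The use formula as written.** SAP 6.1.7.1 subtracts the returned weight of all six vials from an average dispensed weight. Read literally, with contents of about 8 g per vial and no drug used, it gives 8 − 6 × 8 = −40 g. Sum minus sum, or average minus average, would give 0. At the 30-day maximum those two give 24 g and 4 g before priming, so the text must say which is meant.

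**7. What weights can detect.** Ten days at 8 doses and 20 days at 1 average (80 + 20) / 30 = 3.3 a day. Interval weights therefore find sustained over-use, not single days above the limit.

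**The case against.** A reader might infer that over-use will never be recorded. The documents do not support that. Protocol 13.1.2.2 treats any noncompliance, including the subject's, as a deviation. Staff review eDiary dosing from Visit 3 to Visit 14, deviations are tabulated and listed, and a separate deviation guidance plan, not available here, may say more. SAP 4.1 gives SD, minimum and maximum as well as the mean, and SAP 6.1.8 promises listings of all collected data. The table shells are not in the available text. All of this stands. What remains is that no stated rule compares use with the maximum, and the daily record on which site judgement would rest is one the SAP calls unreliable.

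A reader might also infer from the kit size that subjects took too much. That does not follow. The six vials appear only in the SAP, in wording that matches text the Protocol amendment superseded. The factor of 2.0 assumes every millilitre is delivered. Part of any surplus has a stated reason, since Protocol 9.9.1 calls for a fresh vial each week, and a week at the maximum takes 4 × 2 × 7 = 56 sprays against at least 60 per vial.

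Finally, a reader might infer that uncounted over-use makes the drug look safer than it is. Over-use would tend to add AEs, not hide them. Uncounted under-use threatens the exposure claim at least as much, because days of exposure accrue regardless of dosing.

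**Conclusion.** The point holds as a gap in the exposure analysis. No planned analysis relates a subject's use to the maximum of 4 doses a day, in either direction, and the level of use in SAP 5 is undefined. Mean, SD, minimum and maximum in weight units, unadjusted for interval length, cannot supply the missing counts.

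If the SAP's 6-vial kit applies, the supply is about 1.5 times the 30-day maximum at 60 sprays per vial and at most 2.0 times if all 8 mL is delivered. With fewer vials or longer intervals the ratio is lower, so the SAP and the current Protocol must be reconciled on kit size. The ratio is evidence of opportunity only. The documents contain no data on how often over-use or very low use occurs.

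The change is worth making because it is cheap and affects what the report can say about safety at up to 4 doses a day.

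**What to change.** In SAP 6.1.7.1 and 7.4, replace the weight difference with a variable for each subject and dispensing interval:

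average doses per day = (total dispensed weight − total returned weight over the same vials − priming allowance) / (density × 0.2 mL × actual days between visits).

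- State the density and the priming allowance. The current Protocol gives no priming volume, so the allowance should come from the instructions supplied with the product.
- Sum over all vials dispensed in the interval rather than fixing the number at six. Protocol 9.9.1 allows additional supply between visits.
- Treat intervals with unreturned vials as not evaluable, and report how many there are.
- In Table 14.1.5.2, show the distribution of this variable, including very low use, and n (%) of subjects with any interval average above the Protocol's own maximum.
- List those subjects' AEs, and use the same variable to define the level of use in SAP 5.
- Send flagged intervals to deviation review. They should not become important deviations automatically.
- Record in SAP section 10 that the dose summaries of Protocol 13.1.3 are replaced by this weight-based measure.

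The cost is SAP wording, one derived variable and one listing, all from weights already in the eCRF. The drawbacks are that only sustained over-use is detected, and that spillage or extra priming will produce some false flags.

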7.5. Exploratory Efficacy Analysis

All exploratory endpoints will be summarized for descriptive purposes only.

The following variables will be summarized for all subjects completing each visit. All derived variables will be computed as described in Section 0.

Categorical data will report frequency of responses and proportion of responders by study visit:

1. Proportion of CGI-I responders will be assessed from Visit 3 to Visit 14 by study visit.
2. Change in proportion of PGI-C responders will be assessed from Visit 3 to Visit 14 by study visit.
3. Proportion of CGI-S scores > 4 by from Visit 2 to Visit 14 by study visit.

Continuous data will report descriptive statistics of observed values and change from baseline by study visit:

4. Change in LSAS total scores by visit.
5. [REDACTED]

8. Safety and Tolerability Analysis

Safety in this study will be evaluated based on data collected on AEs, clinical laboratory assessments, vital signs, 12-lead ECGs, PWC-20 (at Visit 14/15 End of Study/Follow-up), and physical examinations including examination of the nasal passages. As a precautionary measure, subjects will also be assessed using the C-SSRS and HAM-D at each study Visit.

All safety analysis reporting will be based on the Safety Population (as defined in Section **Error! Reference source not found.**). No formal statistical testing will be conducted for the safety analyses. Descriptive statistics will be used to evaluate safety data. Summaries will present data by overall subjects. Listings will list safety data by subject.

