STATISTICAL METHODS	
Analysis Populations:
 
Safety population: All subjects who receive IP.
 
All analyses will be performed using the Safety population.
 
Safety Analyses:
 
Safety and tolerability implications are best addressed by applying descriptive statistical methods to the data, supplemented by calculation of confidence intervals wherever this aids interpretation. The incidence of AEs for defined periods of exposure (e.g., 3 months, 6 months, 9 months, 12 months, and overall) will be evaluated in the form of a proportion relating number of subjects experiencing events to number of subjects at risk for AEs by organ, relatedness, severity of reported AE, and by frequency of AE. In addition, frequency-type of reported AEs (once, continuous, or adaptability to treatment) by time of occurrence after Visit 2 dispensation may be tabulated. These data will be summarized and tabulated, including confidence intervals when appropriate, for descriptive purposes, and may serve as nonparametric endpoints. Time series analysis will be used where warranted to determine whether frequency of AEs changes with increased duration of exposure.
 
Efficacy Analyses:
 
Exploratory endpoints address efficacy using patient- and clinician-rated scales and will be evaluated for significant changes from baseline using a generalized linear model for repeated measures.

SAMPLE SIZE DETERMINATION	
Based on feedback from the FDA, the sample size for this study (up to 600 subjects) has been selected to attain a PH94B safety database per the ICH E1 Guideline.

STUDY AND TREATMENT DURATION	
The sequence and maximum duration of the study periods will be as follows:
 
 
1. Screening and washout (if applicable): From 7 to 35 days
 
2. 12-Month treatment period: From Visit 2 (Baseline) through Visit 14 (End of Treatment)
 
3. Follow-up period: Follow-up visit (Visit 15) conducted approximately 2 weeks after last treatment
 
 
The maximum study duration for each subject is approximately 59 weeks.
 
The maximum treatment duration for each subject is 12 months.

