### 13.1. Statistical Analysis

This section presents a summary of the planned statistical analyses.

Safety, tolerability, and efficacy variables will be summarized using descriptive statistics. Descriptive summaries for categorical variables will include count and percentage. Descriptive summaries for continuous variables will include number of subjects (n), mean, standard deviation (SD), median, minimum, and maximum. Where appropriate, 95% confidence intervals (CIs) may be reported. Summaries will be presented by time point. All CIs will be 95%, unless stated otherwise.

Unless specified otherwise, all data recorded, will be listed by subject. A comprehensive description of planned analyses and statistical considerations will be described in the statistical analysis plan (SAP).

Summary statistics will be reported based upon observed data. Should a determination of treatment period be required for an AE or concomitant medication when the corresponding date is missing, or is a partial date, the event/medication will be considered as “on-treatment” unless the portions of the date that are available indicate that this is not possible.

Details of the planned analyses, including strategies if needed to assess and address consequences of the COVID-19 pandemic on study conduct and study data, will be provided in the SAP that will be finalized before the database is locked.

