#### 13.1.5.1 Exploratory Endpoints

Overall subject improvement as assessed by the clinician's rating on LSAS, CGI-S, CGI-I, and the subject's rating of the PGI-C from Screening (Visit 1) through Follow-up (Visit 15) will be summarized, including changes from baseline where appropriate. The change in LSAS, CGI-I, and PGI-C scores from Baseline to Visit 14 may also be explored using generalized linear model for repeated measures.

In addition, overall change in the pattern in the frequency of PH94B use (frequent users; 3 or 4 times a day and less frequent users;  $\leq$  2 times a day), change in medication use as documented by the clinician and the subject between Screening (Visit 1) and Follow-up (Visit 15) will be summarized.

Full details on this exploratory analysis will be provided in the SAP.

The exploratory endpoints are as follows:

- Change in total LSAS scores over time with use of PH94B
- Change in proportion of subjects with CGI-S scores  $>4$  over time with use of PH94B
- Change in proportion of subjects with CGI-I scores of 1 (Very much improved) or 2 (Much improved) over time with use of PH94B
- Change in proportion of subjects with PGI-C scores of 1 (Very much improved) or 2 (Much improved) over time with use of PH94B
- [REDACTED]
- [REDACTED]
- [REDACTED]

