6.1.4. Handling of Dropouts or Missing Data

Only observed data will be included in the final report.

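### By-visit efficacy summaries use only subjects completing each visit, with no repeated-measures model, so response-related dropout could move the figures in either direction without any true change

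*SAP*

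**What the plan says.** **Denominator.** SAP 7.5 introduces the four scales with "The following variables will be summarized for all subjects completing each visit" and adds "All exploratory endpoints will be summarized for descriptive purposes only". The set of subjects behind each figure can therefore change from visit to visit.

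**Missing data.** SAP 6.1.4 says "Only observed data will be included in the final report". Protocol 13.1 had already taken that line: "Summary statistics will be reported based upon observed data". The SAP gives no imputation or sensitivity analysis.

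**Model.** The protocol synopsis says the exploratory endpoints "will be evaluated for significant changes from baseline using a generalized linear model for repeated measures". Protocol 13.1.5.1 says that LSAS, CGI-I and PGI-C "scores from Baseline to Visit 14 may also be explored using generalized linear model for repeated measures", and leaves full details to the SAP. The SAP specifies no such model.

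**Declared changes.** SAP Section 10 does not mention the model. Its nearest entry, which cites limited data, is "A qualitative review of categorical data was done instead of an assessment of a change in proportion over time". That entry concerns categorical data, so it does not cover LSAS.

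**Visit 14.** Protocol 7.1 gives the early-termination visit the Visit 14 label. Protocol 10.2.3 includes LSAS, CGI-S, CGI-I and PGI-C among its assessments. SAP 6.1.5 assigns analysis visits by nominal visit. The SAP does not say whether early-termination ratings enter the Visit 14 row.

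**The concern.** These endpoints are read as a course over 12 months. When each visit has its own denominator, a change between visits can reflect who is still attending as well as how subjects are doing. If subjects who do not benefit leave sooner, the responder proportion rises and mean LSAS change grows with nobody improving. If subjects who do well leave sooner, the opposite happens.

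The protocol gives some reason to expect a link. Section 8.3 lists disease progression as a ground for withdrawal. Section 9.7.2 discontinues a subject who comes to need benzodiazepines for anxiety. Section 8.4 says withdrawn subjects are not replaced.

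SAP Section 1 allows these analyses to go into study reports, submissions or manuscripts. A by-visit curve without a fixed denominator or a model beside it could be read there as sustained or growing benefit.

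**Working it through.** The documents state no figure to reproduce. The sample size (up to 600) is set by safety exposure, and no response rate, dropout rate or LSAS standard deviation is given. **All inputs below are assumptions, apart from N = 600 in step 4.**

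**1. Responder proportion with no true change.** Fix each subject's responder status. Let p be the true proportion, and r and h the monthly dropout in responders and non-responders. After m months:

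observed proportion = p(1−r)^m / [p(1−r)^m + (1−p)(1−h)^m]

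Take p = 0.45 and r = 0.02.

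| h | Month 11 (Visit 13) | Month 12 | Still in study, month 12 |
|---|---|---|---|
| 0.04 | 0.3603/(0.3603+0.3510) = 50.7% | 0.3531/(0.3531+0.3370) = 51.2% | 69% |
| 0.06 | 0.3603/(0.3603+0.2785) = 56.4% | 0.3531/(0.3531+0.2618) = 57.4% | 61% |
| 0.10 | 0.3603/(0.3603+0.1726) = 67.6% | 0.3531/(0.3531+0.1553) = 69.4% | 51% |

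The month-12 column applies only if early-termination ratings are kept out of that row.

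**2. Reversed direction.** With h = 0.02 and r = 0.04, month 12 gives 0.2757/(0.2757+0.4316) = 39.0%. With r = 0.06 it gives 0.2142/(0.2142+0.4316) = 33.2%. With equal dropout it stays at 45%.

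**3. Early-termination ratings counted at Visit 14.** If every dropout attends and is counted, the Visit 14 numerator and denominator again cover all subjects, and the proportion returns to the true 45%. The row then mixes ratings made after a month or two with ratings at a year. Visits 4 to 13 are unaffected and keep the drift.

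**4. LSAS change, simulated.** N = 600, 15 replicates. True mean change is −15 at every month, between-subject SD 20, residual SD 10. Monthly dropout has logit −3.3 + k × (last observed change + 15)/20, so k > 0 means poorer responders leave more.

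| k | Retained | Observed mean, month 12 | Mixed model, month 12 | Dropouts' last rating counted at Visit 14 |
|---|---|---|---|---|
| 0 | 67% | −14.4 | −14.8 | −15.0 |
| 0.5 | 65% | −19.3 | −15.2 | −14.4 |
| 1.0 | 59% | −23.0 | −14.9 | −13.1 |
| −0.5 | 65% | −11.1 | −15.2 | −16.0 |

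At k = 0 dropout is unrelated to response by construction, so −14.4 differs from −15 only by simulation error. The standard error there is about √(20²+10²)/√(600×0.67)/√15 = 0.29.

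The mixed model recovers the true value because dropout here depends only on observed ratings. Generalized estimating equations with independence working correlation gave −19.3 at k = 0.5, the same as the raw observed mean. The protocol's model name does not say which type is meant, so that wording alone does not secure a correction.

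**5. Counting dropouts as non-responders.** The proportion is p(1−r)^m: 0.45 × 0.98 = 44.1% at month 1 and 0.45 × 0.98^12 = 35.3% at month 12, again with no true change. It works as a lower bound but is not an unbiased estimate.

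**The case against.** The strongest opposing case is that little depends on this. Protocol 7.2 makes efficacy exploratory, in an open-label study without a comparator, with formal evaluation in two other Phase 3 studies. The SAP calls the summaries descriptive and its tests exploratory. SAP 4.1 already requires n for continuous summaries, and SAP 7.1 tabulates withdrawals and reasons by time in study. Section 10 also steps back from assessing proportions over time. All of this stands, and it limits the severity.

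Three stronger readings are tempting, and the documents do not support them.

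- *A committed model was dropped.* The synopsis wording is firm, but 13.1.5.1 says only that the scores "may also be explored using generalized linear model for repeated measures". Observed-data summaries were in the protocol from the outset. What remains is an unresolved conflict within the protocol and an unrecorded omission in the SAP.
- *The plan will make efficacy look better than it is.* That needs non-responders to leave more often. The rules in 8.3 and 9.7.2 remove some worsening subjects, but no rate is given, other withdrawals (such as pregnancy) can be unrelated to response, and responders may leave by choice.
- *The month-12 result in particular is inflated.* Early-termination ratings may sit in the Visit 14 row and offset the drift.

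Counting every dropout as a non-responder is also no neutral remedy, since it forces a decline.

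**Conclusion.** The point holds in a limited form. By-visit efficacy rests on a set of subjects that may shrink, with observed data only and no model. The protocol is inconsistent about whether a model is used, and SAP Section 10 does not record its absence.

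If dropout is related to response, the by-visit figures can drift with no true change. Under the assumed rates, a constant 45% would read 51% to 69% by month 12 when non-responders leave more, and 39% or 33% when responders do. Those month-12 values also assume that early-termination ratings are kept out of the row. The drift is clearest at Visits 4 to 13. At Visit 14 it may be offset, at the price of mixing early and 12-month ratings.

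Direction and size cannot be settled from the documents. No primary conclusion and no sample size depends on this. It is worth correcting because the correction needs no new data.

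**What to change.** Keep the observed-case summaries and add the following, all labelled exploratory:

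1. **LSAS change:** a likelihood-based mixed model for repeated measures in the Safety population, with visit, baseline LSAS and a within-subject covariance structure, using all observed visits. State the missing-at-random assumption.
2. **Early termination:** state that these assessments are assigned to the visit nearest their actual date and not to month 12. This needs a stated exception to the nominal-visit rule in SAP 6.1.5.
3. **CGI-I and PGI-C:** beside each observed-case rate, show responders over all treated subjects with a 95% confidence interval. Label it a conservative lower bound, not a replacement.
4. **Documents:** reconcile the synopsis with protocol 13.1.5.1, and record the change to the model in SAP Section 10.

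The cost is a little more programming. Later-visit figures may look less favourable, and the lower bound falls mechanically with any dropout, whatever its cause. The mixed model corrects the drift only as far as missing at random is reasonable.
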